## 6.2. Safety Endpoints

- Adverse events, including monitoring of targeted events including, but not limited to:
  - Anticholinergic effects such as dry mouth, dry eyes and constipation.
  - CNS effects such as behavioral changes (eg, aggression), decreased cognitive function, headache, seizures, somnolence.
  - Visual effects such as accommodation disorder, blurred vision, and amblyopia.
- Visual acuity and accommodation tests.
- Cognitive function by the Child Behavior Checklist and Grooved Pegboard Test.
- Vital Signs, including heart rate in the context of age-appropriate norms.

- Urinary Tract Infection, as evidenced by urinalysis, urine microscopy, culture and sensitivity.
- Clinical Laboratory Evaluations in the context of age-appropriate norms, with particular reference to liver function tests and renal chemistry.
- Post-void residual volume (PVR) in subjects not performing CIC, or with >1 urinary tract infection (UTI) during the study.
- Physical Examination and weight.

### **6.2.1. Adverse Events**

Adverse event information will be collected for all subjects. Information that will be collected includes: nature of event, whether event was serious; date of onset; date of cessation or event continuing; severity of event; relationship of event to study drug; action taken regarding study drug due to the event; clinical outcome of event.

A 3-tier approach will be used to summarize AEs. Under this approach, AEs are classified into 1 of 3 tiers. Different analyses will be performed for different tiers (See [Section 8.2.5](#)).

Tier-1 events: These are pre-specified events of clinical importance and are maintained in a list in the product's Safety Review Plan.

Tier-2 events: These are events that are not tier-1 but are "common". A MedDRA PT is defined as a tier-2 event if there are at least 4 subjects in any treatment group.

Tier-3 events: These are events that are neither tier-1 nor tier-2 events

### **Visual acuity and accommodation tests**

*Visual acuity will be assessed using the Snellen method, using an optotype that is appropriate to the child's intellectual development at Visit 2, Visit 5, and Visit 7.*

Amplitude of accommodation will be assessed by the push up test to assess minimum focusing distance at Visit 2, Visit 5, and Visit 7. The subject will focus on a single letter of the 20/40 line of an eye chart (appropriate optotype) and this will be moved slowly toward the subject until it blurs. At this point the distance from eye to letter will be measured for each eye.

For both visual acuity and accommodation assessments the same optotype will be used for a specific subject throughout the study to ensure standardization and validity.

### **6.2.2. Vital Signs**

*Blood pressure, temperature and pulse rate should be measured at Visit 1, Visit 2, Visit 3, Visit 5 and Visit 7. This schedule of measurements should provide adequate indication of any clinically relevant changes. However, if vital signs show a clinically relevant change from baseline, then safety monitoring will occur at a minimum of monthly intervals, or more frequently as clinically appropriate, until the abnormality*

*resolves. The measured results will be assessed in the context of age appropriate norms.*

*Temperature may be taken via oral, tympanic or axillary routes as per local accepted practice. Digital devices are permitted; however, mercury thermometers should not be used. The same method should be used for the subject throughout the study.*

*Blood pressure should be measured using a pediatric or appropriately sized sphygmomanometer in the sitting/resting position with the subject's arm supported at the level of the heart, and recorded to the nearest mmHg. The same arm (preferably the dominant arm) will be used throughout the study.*

*The same size blood pressure cuff, which has been properly sized and calibrated, will be used to measure blood pressure each time. The use of automated devices for measuring BP and pulse rate are acceptable, although, when done manually, pulse rate will be measured in the brachial/radial artery for at least 30 seconds.*

### **6.2.3. Physical Exam**

*A physical examination will be performed at V1/Screening, and will include the following systems:*

- *General appearance (including weight).*
- *Skin.*
- *HEENT (head, eyes, ears, nose, throat, visual acuity and accommodation).*
- *Respiratory.*
- *Cardiovascular.*
- *Gastrointestinal.*
- *Musculoskeletal.*
- *Neurourological.*

*Additional physical assessments will be performed as necessary to evaluate the subject. Any clinically significant negative changes from the entry examination will be recorded as adverse events.*

### **6.2.4. Weight Measurements**

*Weight will be recorded at Screening and used to assess eligibility and for stratification purposes. Subsequently weight will be recorded at Visit 3, Visit 5, and Visit 7. All weight measurements should be standardized using the same equipment and measuring technique for an individual subject. Any clinically significant change in weight should be reported as an adverse event.*

### 6.2.5. Electrocardiogram

*Scheduled ECGs should be performed after the subject has rested quietly for at least 10 minutes in a supine position. A single 12-lead ECG will be obtained on all subjects at screening.*

### 6.2.6. Clinical Laboratory Evaluation

*The following safety laboratory tests will be performed at Visit 1 (Screening) and additional visits as below, or as needed to follow-up on significant findings.*

#### Safety Laboratory

| Hematology – V1, V5, V7   | Chemistry - V1, V5, V7   | Urinalysis – V1, V3, V5, V7  | Other  |
|---|--|--|--|
| Hemoglobin
Hematocrit
RBC count
Platelet count
WBC count with differential as below:
Total neutrophils (Abs)
Eosinophils (Abs)
Monocytes (Abs)
Basophils (Abs)
Lymphocytes (Abs) | GOT (AST)
GPT (ALT)
Total bilirubin
Alkaline phosphatase
LDH
CPK
BUN
Creatinine c
Uric acid
Total protein
Sodium
Potassium
Corrected calcium
Glucose | Urine will be tested for the following using a urine dipstick:
pH
Specific gravity
Leukocyte esterase
Nitrites
Glucose
Protein
Blood
Ketones

Urine microscopy, culture and sensitivity a | Pregnancy Test b (serum V1, urine at subsequent visits, 2, 3, 5, and 7)
Unanonymized pharmacogenomic sample (V3 only) d
PK sample (V3 only) d |

a Urine microscopy, culture and sensitivity to be performed in the event of the presence of symptoms (eg, fever, flank pain), positive leucocytes and/or nitrites on urinalysis, or if the subject has a documented history of vesicoureteral reflux (VUR).

Subjects who are found to have an active UTI during screening as defined in exclusion criterion 12 may continue screening activities on resolution of symptoms or treatment of the UTI to the satisfaction of the treating physician.

b Females of childbearing potential only (≥9 years old or have experienced menarche, whichever is earlier). Pregnancy tests may also be repeated as per request of IRB/IECs or if required by local regulations.

cWhen indicated, the investigator may request calculation of an estimated GFR using the Schwartz equation  $GFR = (k \times H)/Cr$  where k = constant, H = Height (length) and Cr = Creatinine. In this case, the laboratory will need to be provided with the subject's height in cm.

d PG and PK samples are for fesoterodine group subjects only.

### 6.2.7. Childhood Behavior Checklist (CBCL)

*The CBCL is a questionnaire by which a child's problem behaviors and competencies can be assessed. This instrument can either be self-administered or administered through an interview. The CBCL can also be used to measure a child's change in behavior over time or following a treatment. The first section of this questionnaire consists of 20 competence items and the second section consists of 120 items on behavior or emotional problems. For the purpose of this trial, subjects will be asked to complete 113 items on behavior and emotional problems.*

*The CBCL will be completed at Visit 2, Visit 5 and Visit 7.*

### **6.2.8. Grooved Pegboard Test (GPT)**

*The Grooved Pegboard Test is a manipulative dexterity test that assesses psychomotor speed, fine motor control, and rapid-visual motor coordination. It consists of a small board of 25 holes with randomly positioned slots. Pegs with a key along one side must be rotated to match the hole before they can be inserted. Time to completion is scored, and higher scores represent lower levels of performance.*

*The GPT will be assessed at Visit 2, Visit 5 and Visit 7.*

### **6.3. Pharmacokinetic Evaluations**

*Variation in the CYP2D6 gene plays a role in metabolism of active metabolite (5-HMT) of fesoterodine. The alleles which will be genotyped are \*3, \*4, \*5, \*6, \*7, \*8, \*10, \*14, \*17, \*18, \*21, \*36, \*41 and duplication. Homozygous or heterozygous combinations of \*3, \*4, \*5, \*6, \*7, \*8, \*14, \*17, \*18, and \*21 will be classified as poor metabolizer (PM) of CYP2D6. Other genotypes will be classified as extensive metabolizer (EM). CYP2D6 genotype and metabolizer status of subjects randomized to fesoterodine treatment will be reported as an individual-subject listing.*

For those subjects who are randomized to fesoterodine and who do not have sufficient laboratory documentation, a 2-ml whole blood sample will be collected for CYP2D6 genotype analysis. All samples will be discarded following analysis. Subjects who have prior laboratory documentation of their CYP2D6 genotype will not be required to submit a blood sample for pharmacogenomics. Subjects randomized to treatment with oxybutynin will also not be required to provide a sample for pharmacogenomic assessment.

Population pharmacokinetic analyses will be conducted via nonlinear mixed-effects modeling with the NONMEM® software, Version VI (ICON Development Solutions, [name]). Model-based parameter estimates for absorption rate constant (Ka), apparent oral clearance (CL/F) and volumes of distribution (Vd) will be determined to predict the area under the curve (AUC), maximum concentration (Cmax), time to reach Cmax (Tmax) and half-life of 5-HMT in patients randomized to fesoterodine treatment. Possible influences of patient covariates (eg, age, body weight, gender, CYP2D6 metabolizer status etc.) on 5-HMT exposure will be assessed.

### **6.4. Covariates**

The baseline observation for the endpoint being analyzed will be used as a continuous covariate in any ANCOVA analyses.

Baseline weight will be used as a continuous endpoint in any ANCOVA analyses.

The following subgroups will be assessed for the primary endpoint:

Age: Ages  $\geq 6-9$ ,  $\geq 10-12$ ,  $\geq 13-17$

Weight: Cohort 1:  $\leq 50$  kg,  $>50$  kg, Cohort 2:  $\leq 20$  kg,  $>20$  kg

Gender: Male, Female

Region: Cohort 1: North America, Europe, Asia, Cohort 2: North America and Europe, Asia

Type of Underlying Disease: Congenital, Acquired, Unknown

Race: White, Asian, Black, Other (where Other includes: American Indian or Alaska Native, Native Hawaiian or other Pacific Islander)

Ethnicity: Hispanic/Latino, Not Hispanic/Latino

Underlying disease will be categorised as 'congenital' or 'acquired' and will be determined through manual review of medical history listings (by the clinician) for Cohort 1. If this is unable to be determined, this will be categorized as 'Unknown'. For Cohort 2 the answer to the question "Underlying Cause of Primary Diagnosis" on the Primary Diagnosis eCRF page will be utilized, for which the responses are 'Congenital' or 'Acquired'.

## 7. HANDLING OF MISSING VALUES

### Missing visits

For the PPAS analysis no imputation techniques for missing data will be employed. For the FAS analysis a combination of Baseline Observation Carried Forward (BOCF) and a Last Observation Carried Forward (LOCF) algorithm will be used for missing data. For example, where a subject has no post-baseline observation then the baseline observation will be carried forward and used for Week 12 analyses; if a subject withdraws early then their termination visit will be carried forward (note this will be labelled as 'Week 12' in the dataset).

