#### **6.4. Dose Optimization of Oxybutynin (Weeks 1, 2 and 3, $\pm 2$ days) (Subjects $>25$ kg)**

Subjects randomized to oxybutynin will have their dose adjusted at weekly intervals during the first 4 weeks of the study. Only oxybutynin tablets of one dosage strength will be dispensed at Visit 2. There should be a minimum of 3 contacts between V2 and V3 to assess efficacy and tolerability. The contacts with the subject's parent/guardian (caregiver) may be by telephone calls or clinic visits as considered clinically appropriate following assessment by the investigator. The investigator will record dose adjustments in the medical records and CRF, and the caregiver will keep a telephone appointment and dosing log, to record the instructions they have been given. In addition, within a few days of any change in oxybutynin dose, there should be verification that caregivers have correctly understood the change in the subject's dose regimen eg, by telephone contact, or by confirmation of dosing information captured in the subject's dosing log.

Subjects randomized to oxybutynin will receive oxybutynin extended release (XL) tablets at a starting dose in accordance with approved pediatric labeling, and accepted practice eg, oxybutynin XL 5 mg once a day. Dose optimization will be achieved by either up- or down-titration in 5 mg increments on an approximately weekly basis to achieve a balance of efficacy and tolerability. Subjects who were on oxybutynin prior to study entry and who are randomized to the oxybutynin XL treatment group may, at the discretion of the investigator, restart at the equivalent pre-study total daily dose.

Subject's caregivers should receive a contact approximately 1 week after starting oxybutynin to assess efficacy and tolerability, and to adjust the dose as appropriate. Healthcare professionals deciding the dose adjustments must be medically-qualified and have prescribing authority, eg, MD. Qualifications of delegates will be reviewed and agreed with the Pfizer study team as part of the standard site pre-trial assessment procedure, and prior to any subject enrollment.

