## **6.12. Subject Withdrawal**

In France, see [Appendix 5](#).

If treatment is inadequate or the subject cannot tolerate the dose of fesoterodine or oxybutynin, consideration should be given to withdrawal.

Subjects who withdraw from the oxybutynin treatment arm (Cohort 1, >25 kg) for reasons of toleration, and who fulfill all continuation criteria, may be directly allocated by the investigator to fesoterodine treatment at either 4 mg or 8 mg/day for the remaining 12 week safety extension period if appropriate. All subsequent study visits should be scheduled relative to the start of the extension phase.

Subjects may withdraw from the study at any time at their own, or their legal representative(s) request, or they may be withdrawn at any time at the discretion of the investigator or sponsor for safety or behavioral reasons, or the inability of the subject to comply with the protocol required schedule of study visits or procedures at a given study site.

If a subject does not return for a scheduled visit, every effort should be made to contact the subject. In any circumstance, every effort should be made to document subject outcome, if possible. The investigator should inquire about the reason for withdrawal, request the subject to return all unused investigational product(s) and electronic diary equipment, request the subject to return for a final visit, if applicable, and follow-up with the subject regarding any unresolved adverse events (AEs).

Subjects in the fesoterodine groups who withdraw prior to Week 4 should have PK samples obtained as per Visit 3.

If a subject withdraws from the study prior to Visit 5 (Week 12), the same assessments as at Visit 5 should be performed if possible. Urodynamic assessment should only be performed in subjects who have been on a stable dose of study medication for at least 2 weeks, and who have not missed any doses in the 3 days prior to the visit.

If a subject withdraws from the study after Visit 5, the same assessments as at Visit 7 (Week 24) should be performed if possible.

Subjects who withdraw early from the study and who have taken at least 1 dose of study medication should also be contacted by telephone approximately 2 weeks after stopping study medication, and have the same assessments performed as at Visit 8 (Week 26).

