### 9.1. Sample Size Determination

#### *Cohort 1 (>25 kg)*

A sample size of 33 evaluable subjects per group is sufficient to give a power of at least 90% to detect a change from baseline of 70 mL in the primary endpoint, maximum cystometric capacity (MCC), when the standard deviation of the change from baseline is 120 mL. This calculation assumes the testing will be performed at a two-sided 5% significance level and is based on results observed from the two highest dose periods (each 4 weeks) in previous tolterodine neurogenic bladder studies 583E-URO-0581-001, 583E-URO-0581-002 and 583-URO-0581-003, as well as published data from studies of oral oxybutynin in neurogenic bladder subjects. An oxybutynin active comparator arm will enable comparisons between fesoterodine and oxybutynin to be made; therefore a sufficient number of subjects will be randomized into Cohort 1 to ensure a total of approximately 99 subjects (33 evaluable subjects per arm) are evaluable at Week 12.

This sample size will also provide a 2-sided 95% confidence interval for the change from baseline in MCC of approximately  $\pm 70$  mL around the point estimate for the difference between each fesoterodine arm and oxybutynin, with 90% coverage probability. Using this estimation approach, these confidence intervals will be used to assess the comparability of each fesoterodine dose and oxybutynin.

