### Diary Data

For the analysis involving diaries, time-points will be defined as non-overlapping periods. See [Appendix B](#) for definition of time intervals. Missing daily micturition data will be estimated as the following:

1. If one out of three days is missing, the mean of the remaining days will be used to impute the micturition data for the missing day/days.
2. The LOCF/BOCF imputations will be carried out for time-intervals with missing diary data. For intervals where less than two days of diary data are available, the previous available 3-day post-baseline interval values will then be carried forward.

Micturition volume is collected on one day only therefore if it is missing at a visit the previous visit's data will be carried forward.

Note: In subjects who withdraw after a minimum of 2 weeks of treatment, attempts should be made to perform a urodynamic assessment, provided that they have not missed any doses in the three days previous to the visit.

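### In the Cohort 1 FAS, whether an early withdrawal is scored by BOCF or LOCF depends on the arm between about Weeks 2 and 6, which tilts the secondary fesoterodine-oxybutynin differences slightly toward fesoterodine

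*SAP*

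**What the plan says.** Urodynamics are scheduled only at Visit 2 and Visit 5, so a subject who leaves before Week 12 has a post-baseline MCC only if a termination test is done.

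- **Imputation (SAP 7, Missing visits).** In the FAS, "where a subject has no post-baseline observation then the baseline observation will be carried forward and used for Week 12 analyses", but "if a subject withdraws early then their termination visit will be carried forward". SAP 5.1 keeps subjects with baseline data only, so these zeros enter the ANCOVA.
- **When a withdrawal test may be done (Protocol 6.12).** "Urodynamic assessment should only be performed in subjects who have been on a stable dose of study medication for at least 2 weeks"; no dose may have been missed in the three days before. Protocol 7.1.1 and footnote b of the schedule, repeated in SAP Appendix A, say the same.
- **A different condition (SAP 7, Diary Data note).** "In subjects who withdraw after a minimum of 2 weeks of treatment, attempts should be made to perform a urodynamic assessment". The three-day condition is kept, but a stable dose is not mentioned.
- **Dose changes by arm.** Fesoterodine 4 mg has none and 8 mg has one, at Week 1 (Protocol 5.1). For the comparator, Protocol 6.4 states: "Subjects randomized to oxybutynin will have their dose adjusted at weekly intervals during the first 4 weeks of the study". The dose is then fixed, and subjects who cannot tolerate 10 mg are to be withdrawn. Previous users may restart at their pre-study dose (Protocol 5.2).
- **Status of the contrast (SAP 8.2.1).** The differences between each fesoterodine dose and oxybutynin are secondary and read from point estimates and 95% confidence intervals, without formal testing. The primary comparisons are the within-arm changes on fesoterodine.

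**The concern.** Each rule is reasonable alone. Together they make the imputed value depend on the arm. Two children may leave in the same week with the same underlying gain. The one on fesoterodine can be tested and keeps that gain; the one on oxybutynin whose dose changed ten days earlier cannot be tested and is scored zero. The rule on 10 mg intolerance also places some oxybutynin withdrawals in this period.

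What is at stake is the only between-arm efficacy comparison planned. It serves a stated secondary objective, and it is the reason Protocol 9.1 gives for recruiting the oxybutynin arm at this size. Since it is read from the estimate and its interval, a shift in the estimate passes directly into the conclusion.

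**Working it through.** **Inputs from Protocol 9.1.** 33 evaluable subjects per arm; SD of change 120 mL; power and effect stated as "sufficient to give a power of at least 90" per cent and "to detect a change from baseline of 70 mL in the primary endpoint"; "This calculation assumes the testing will be performed at a two-sided 5% significance level".

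**Reproducing the plan's figures.** For a one-sample t-test on the change, the noncentrality is 70 / (120/√33) = 3.35. Power is 90.1% at n = 33 and 89.2% at n = 32, so the stated size is reproduced as a within-arm calculation. For the difference between arms, SE = 120 × √(2/33) = 29.5 mL. The expected 95% half-width is t(64) × 29.5 = 59.0 mL, or 65.5 mL with 90% assurance, in line with the plan's approximate ±70 mL.

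**Earliest withdrawal test = last dose change + 2 weeks.**

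| Arm | Last dose change | Earliest test |
|---|---|---|
| Fesoterodine 4 mg | none | Week 2 (Day 15) |
| Fesoterodine 8 mg | Week 1 | Week 3 (Day 22) |
| Oxybutynin | none; Week 1; 2; 3; 4 | Week 2; 3; 4; 5; 6 |

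Before Week 2 every arm scores zero. After about Week 6 every arm can hold a measured value. The arms differ only from Week 2 (against 4 mg) or Week 3 (against 8 mg), and only for oxybutynin subjects with a dose change in the preceding two weeks. Adjustment contacts are scheduled at Weeks 1, 2 and 3, so the window normally closes at Week 5 (Day 36). It reaches Week 6 (Day 43) only if a change is made at Week 4 itself, which the text permits but does not schedule.

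**Size of the shift.** Let q be the share of the oxybutynin arm scored zero only because of the stable-dose condition, and G the gain those subjects would otherwise have kept. The difference, fesoterodine minus oxybutynin, moves by q × G. One subject in 33 at G = 70 mL gives 70/33 = 2.1 mL (1.1 mL at G = 35; 3.0 mL at G = 100).

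**Scenarios (assumptions).** Neither dropout nor its timing is in the documents. Below, G = 70 mL and every oxybutynin withdrawal in Weeks 2-6 is taken as affected. Uniform timing puts 4/12 of withdrawals in that window. The last column is 1 − Φ(1.96 − shift/29.5), the chance that the 95% interval lies wholly on fesoterodine's side when the drugs are equal; without the shift it is 2.5%.

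| Dropout by Week 12 | Share in window | q | Shift | Interval favours fesoterodine |
|---|---|---|---|---|
| 10% | 4/12 | 3.3% | 2.3 mL | 3.0% |
| 20% | 4/12 | 6.7% | 4.7 mL | 3.6% |
| 30% | 4/12 | 10% | 7.0 mL | 4.2% |
| 10% | 60% | 6% | 4.2 mL | 3.5% |
| 20% | 60% | 12% | 8.4 mL | 4.7% |
| 30% | 60% | 18% | 12.6 mL | 6.3% |

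**The case against.** **Not every oxybutynin withdrawal is affected.** A subject kept on the starting dose, or restarted on an unchanged pre-study dose, qualifies for a test from about Day 15, like fesoterodine 4 mg. A single change at Week 1 matches fesoterodine 8 mg. Fesoterodine subjects also score zero if no test is done or a dose was missed in the last three days. All this stands, and it makes the scenarios above lean high.

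**Some may be tested anyway.** Oxybutynin subjects who leave for intolerance may move to fesoterodine if they meet the continuation criterion, which is urodynamic (Protocol 4.3). That may prompt an exit test and shrink the effect. But the stable-dose condition restricts the same test, so the documents do not settle who will have a value.

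**The SAP note may govern.** If two weeks of treatment were enough, the dose-change asymmetry would disappear. SAP Appendix A and the protocol say otherwise, so the note cannot be relied on to remove it.

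**The PPAS and the descriptive summaries are not imputed.** True, but the PPAS admits only subjects who completed the phase, so it omits these withdrawals and does not test how they are handled.

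**Stronger readings.** A reader might infer that all same-time withdrawals are treated differently; the asymmetry is confined to the window and to recent dose changes. A reader might also put a total dropout of 10-20% straight into 70 × p and get 7-14 mL. Here p is the share of the whole arm leaving inside the window, so with uniform timing those values need 30-60% dropout (10% ÷ 4/12 = 30%; 20% ÷ 4/12 = 60%). Nothing in the documents supports such rates.

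**Conclusion.** The point holds in a limited form. In the Cohort 1 FAS ANCOVA the imputed value depends on the arm for withdrawals from about Week 2 or 3 to about Week 5-6. If MCC improves on treatment, the shift favours fesoterodine. At assumed dropout of 10-20% it is about 2-5 mL with uniform timing and 4-8 mL with 60% of withdrawals in the window, rising to about 13 mL at 30% dropout. Against an SE of 29.5 mL and a half-width of 59 mL this is modest, but it is systematic and more subjects would not remove it.

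The sizes rest on an assumed dropout rate and timing, a 70 mL gain already reached at withdrawal, and all oxybutynin withdrawals in the window being affected. A reader might infer that the trial's primary conclusion is biased. The documents do not support that: the primary tests are within-arm, and the affected contrast is secondary with no decision rule attached. The change is still worth making, because no planned analysis tests how these withdrawals are scored.

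**What to change.** Keep the planned FAS analysis as it is. Overriding measured values in that analysis for the contrasts alone would separate the reported differences from the reported LS means. Instead:

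1. In SAP 7 and 8.2.6, add a sensitivity analysis of the two fesoterodine-oxybutynin contrasts with one rule for all three arms. Options, singly or together: multiple imputation under missing at random, treating Week 12 as missing for every withdrawal whether or not a termination test exists; and zero change for every withdrawal before a common cut-off such as Day 43 (nominal Week 4 plus 14 days).
2. Tabulate, by arm and week of withdrawal, how many Week 12 MCC values are observed, carried forward from a termination test, or set to baseline. This shows directly how many subjects are affected.
3. Reconcile the SAP 7 note (two weeks of treatment) with Protocol 6.12 and 7.1.1 and SAP Appendix A (two weeks on a stable dose).

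The cost is SAP wording and some programming, with no change to trial conduct. Some early termination readings, mostly on fesoterodine, would go unused in the sensitivity analysis. The zero-change version will still lower the estimate for an arm with more early withdrawals; that reflects withdrawal itself, not who was eligible for a test, and should be stated beside the result.
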